Title:

**Studying Hemostatic Effect of Axiostat Dressing on Radial Access After Percutaneous
Procedure (AHD)**

NCT02837744

Protocol ID: ABPL/002

Date: 31-Dec-2020

Protocol

Studying Hemostatic Effect of Axiostat® Dressing on Radial Access After Percutaneous Procedure (AHD)

Purpose

To evaluate Safety and Efficacy of Axiostat haemostatic dressing in terms of time to achieve immediate haemostasis, post application complication and comfort levels of patients.

Type of Study

Single Arm, Single Centre, Prospective

Study Population

Patients who undergo trans radial diagnostic or interventional cardiac procedures and who meet all eligibility criteria will be approached for participation in the study.

Inclusion Criteria

1. Age greater than or equal to 18 years.
2. Patient and/or patient's legal representative and/or impartial witness has/have been informed of the nature of the study and agrees to its provision and has provided written informed consent as approved by the Ethics Committee of the investigative site.
3. Iatrogenic puncture
4. Patient who want to undergo radial intervention.
5. All puncture size must be less than 2.5cm.

Exclusion Criteria

1. Prior diagnosis of disease or medical condition affecting the ability of blood to clot (e.g., hemophilia.).
2. Patients with known sensitivity to chitosan (shellfish) used in this study.
3. Patients who, in the opinion of the Investigator, may not complete the study for any reason, e.g. Patient requiring Immediate suturing.
4. Patient is currently participating in an investigational drug or dressing study that has not yet completed its primary endpoint interferes with procedure and assessments in this study.
5. Pregnant women.
6. Patients with hemorrhagic shock.
7. Patient having hemoglobin < 9 g/dl.

Primary Outcome

Time to achieve hemostasis by observing the time at which blood oozing through or from periphery of the dressing stops.

Secondary Outcomes

- (i) Number of patients with rebleeding will be counted
- (ii) Quantity of product used
- (iii) Skin Irritation and Hematoma formation
- (iv) Ease of use of Product
- (v) Patient Comfort Levels

Materials and Methods:

Study Material

Axiostat® - Size: 3.5 cm X 3.5 cm

Axiostat Chitosan Hemostatic dressing belongs to an advanced class of wound dressing that stops bleeding within few minutes of application by providing an active mechanical barrier.

The dressing is approved in Europe (CE Certified) for the closure of arterial access sites and will be used in this study according to the approved application.

Screening Evaluation & Enrolment

Each potential subject who meets the protocol inclusion and exclusion criteria will be given a description of the study dressing, informed about the goals, risks-benefits and then invited to voluntarily participate in the study. Investigator will answer all the questions asked by patient and/or patient's representative. If a patient/patient's representative or impartial witness voluntarily agrees to participate in the study, he/she will read, understand, sign and date the informed consent form prior to the initiation of any study procedure. Each subject is free to withdraw from the study at any time during the study period.

Application of Axiostat

Inspect the puncture site to assess for inclusion in the study.

Make Sure to wear gloves

Open the dressing pack carefully (Axiostat tends to stick with blood on gloves)

- Remove the sheath and apply Axiostat along with the cotton gauze. Allow blood about 1 or 2 ml of blood to come in contact with Axiostat.
- Make sure Axiostat is placed directly above the puncture site.
- Apply pressure with fingers for about 5 minutes until dressing adheres to blood on puncture site and stays in position.
- Apply secondary dressing (as per Institutional care) such as Dynaplast Bandage. Do not remove or move Axiostat from position during this procedure and keep Axiostat in position for at least 30 minutes.
- If bleeding is persistent, then remove the first Axiostat and apply another Axiostat, on puncture bleeding site. Repeat the same procedure of treatment application.
- Failure to achieve haemostasis after two applications will be noted as dressing failure. In case of dressing failure, patient will be treated as per institutional standard of care.

Time, at which blood oozing through or from periphery of the dressing stops, will be considered as achieving haemostasis and will be noted as the efficacy endpoint.

Axiostat can be kept on site for 24 hours.

Removal of Axiostat: Axiostat must be removed by irrigating it with saline solution / water and gently lifting it off.

Patients will be followed up till discharge.

Training: Training will be rendered to four catheterization laboratory (cathlab) operators for application and direction of use of Axiostat as per study protocol.

Adverse Event Reporting

Investigators shall report all adverse events on the Adverse Event Report Form. All Serious Adverse Event (SAE) need to be reported to the sponsor within 24 hours after the investigator becomes aware of the event. SAE reporting will be done using the Event Reporting Form.

All adverse events need to be reported in the Adverse Event Report Form till patient discharge from hospital for the procedure, if any. Ethics Committee (EC) will be notified for any occurrence of SAE as required per local regulations. Sponsor will be responsible to notify any occurrence of SAE to competent authorities, if applicable

Sample Size

From available literature [1], with the assumption that Axiostat® will decrease time to haemostasis by 30%, minimum number of patients needed for study (with alpha 0.05 and power 0.8) was 15 patients. A total of 75 patients will recruited, with drop-out rate of 10%, ~ 67 patients will be included in the study

Statistical Analysis Plan

Pearson correlation analysis will be performed to check the co-relation between primary efficacy endpoint. Independent sample t-test will be performed to compare the mean of hemostasis time between independent categorical variables. A P-value of ≤ 0.05 will be considered to be significant. Secondary endpoint will be analyzed by descriptive statistics.

References:

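### The plan gives dressing failures no value on the primary endpoint and no place in its mean-based analysis; leaving them out would shorten the mean time to haemostasis

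*Combined protocol and SAP*

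**What the plan says.** The study is "Single Arm, Single Centre, Prospective". Under *Primary Outcome* the endpoint is "Time to achieve hemostasis by observing the time at which blood oozing through or from periphery of the dressing stops", and *Application of Axiostat* repeats that definition.

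The same section sets the procedure: "Apply pressure with fingers for about 5 minutes until dressing adheres to blood on puncture site and stays in position". If bleeding persists, a second dressing is applied in the same way. Then: "Failure to achieve haemostasis after two applications will be noted as dressing failure". And: "In case of dressing failure, patient will be treated as per institutional standard of care". No time, censoring rule or imputed value is attached to such a patient.

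Dressing failure is not among the five items under *Secondary Outcomes*. The *Statistical Analysis Plan* is one paragraph. It has a Pearson correlation involving the primary endpoint, a t-test to "compare the mean of hemostasis time between independent categorical variables", a significance level, and descriptive statistics for the secondary endpoints. It defines no analysis set, missing-data rule, time-to-event method or sensitivity analysis.

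On losses, *Screening Evaluation & Enrolment* states "Each subject is free to withdraw from the study at any time during the study period". *Sample Size* states that 75 are recruited and, "with drop-out rate of 10%, ~ 67 patients will be included in the study".

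**The concern.** The endpoint has a value only if oozing stops under the dressing. A patient still bleeding after two dressings has the worst result the study can record, and is the one patient with no value to analyse. A t-test or a correlation cannot use that patient without a number, so there are three ways forward: drop the patient, enter a time reached under other care, or choose a value after the data are seen. The first turns the primary result into time among those in whom the dressing worked. The second credits other care to the dressing. The third is not prespecified.

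This matters more without a control arm. The only benchmark in the plan is a 30% reduction assumed from literature, and the overall mean is the figure a reader would set against it. No listed outcome fills the gap. The quantity of product used does not, because a success on the second dressing and a failure both use two.

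**Working it through.** **The plan's own figure.** 75 × (1 − 0.10) = 67.5, so about 67 reproduces. The allowance is 75 − 67 = 8 patients. *Sample Size* does not say who they are or why they are lost.

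**Effect on the overall mean if failures are dropped.** The documents give no failure rate, mean time or time for a failure, so these are assumptions:
- 75 patients treated, with a mean of 5 minutes in successes.
- f failures, each counted at t minutes. t = 10 corresponds to two pressure periods of about 5 minutes each. t = 30 is an upper illustration.

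All-patient mean = ((75 − f) × 5 + f × t) / 75. With failures dropped, the reported mean is 5.0. Shortfall = 1 − 5.0 / all-patient mean.

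| f | t (min) | All-patient mean (min) | Reported mean too low by |
|---|---|---|---|
| 0 | any | 5.00 | 0% |
| 1 | 10 | (370 + 10)/75 = 5.07 | 1.3% |
| 2 | 10 | (365 + 20)/75 = 5.13 | 2.6% |
| 4 | 10 | (355 + 40)/75 = 5.27 | 5.1% |
| 7 | 10 | (340 + 70)/75 = 5.47 | 8.5% |
| 4 | 30 | (355 + 120)/75 = 6.33 | 21% |
| 7 | 30 | (340 + 210)/75 = 7.33 | 32% |

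**How extreme must it be to imitate the 30% effect?** Let p be the failure proportion and R the failure time divided by the mean in successes. The all-patient mean is 1 + p(R − 1) times the mean in successes. For dropping failures alone to make no reduction look like 30%, 1 + p(R − 1) = 1/0.7, so R = 1 + 0.4286/p. That gives R of about 15.3, 9.6 and 5.3 at p = 3%, 5% and 10%.

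**Subgroup comparisons.** Simulation with 34 against 33 patients and 4,000 runs. Times in successes have the same distribution in both groups (normal, mean 5, SD 1.5).
- Failures 20% against 2%: the t-test on successes rejects in 5.0% of runs; a Wilcoxon test with failures ranked worst rejects in 25.6%.
- Milder contrasts: the worst-rank test rejects in 8.6% at 10% against 2%, 6.6% at 8% against 2%, and 5.4% at 5% against 1%.

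A t-test that omits failures cannot see a difference expressed as failures. The gain from the alternative is material only when that difference is large.

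**Effect on a median.** If failures are kept as not achieved and times are assumed log-normal with a coefficient of variation of 0.4, the median rises by only 1.5%, 2.6% and 5.5% at failure rates of 3%, 5% and 10%. The median alone therefore does not display failures well.

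**The case against.** A reader might infer that the plan excludes failures and drop-outs, that the 10% allowance consists largely of failures, and that the primary result is therefore biased in favour of the dressing. The documents do not support this.

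- **Exclusion is not stated.** The plan is silent. A time reached under other care could be entered, and that would lengthen the mean.
- **Drop-outs are not shown to be failures.** Consent precedes any study procedure, and the puncture site is then inspected to decide on inclusion, so losses between recruitment and inclusion can occur before a dressing is applied. The protocol treats failure as a recorded result. A patient who withdraws after oozing stops already has a time. The direction of any bias from drop-outs is unknown.
- **The favourable direction belongs to the overall mean.** The planned t-test compares subgroups within one arm, and omitting failures there does not inherently favour the dressing. The weakness there is blindness to failures.
- **The large percentages depend on 30 minutes per failure.** In the protocol, 30 minutes is only the minimum time the dressing stays in place. It is not a time to failure. With few failures counted at 10 minutes the effect is small, and with none it is zero.

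All four limits stand. They bear on how firmly bias can be asserted and how large it may be. They do not supply the missing rule.

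**Conclusion.** The point holds as a gap in the plan. The protocol foresees dressing failures, gives them no value on the primary endpoint, does not list them as an outcome, and plans only analyses that need a numeric time. If failures are dropped, the overall mean is too short and flatters the dressing; if they carry a time from other care, the endpoint is no longer a property of the dressing.

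The size cannot be derived from the documents. Under the assumptions above it runs from 0% with no failures, through about 1% to 9% with 1 to 7 failures at 10 minutes, to 21% to 32% with 4 to 7 failures at 30 minutes. Only the most extreme of these cases reaches the 30% the study was sized for. It is not established that failures will be excluded, that the 8 patients of the drop-out allowance are failures, or that the subgroup t-test favours the dressing.

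**What to change.** 1. Define the primary analysis set as every patient in whom a dressing was applied.
2. Analyse time to haemostasis as time-to-event: Kaplan-Meier median, and percentage haemostatic at fixed times stated in advance.
3. Keep dressing failures as not achieved. They stay in the risk set to the end of an observation window, which the plan must state. They are never dropped and never given the time reached under other care.
4. Patients who withdraw after oozing stops keep their observed time. Those who withdraw before it stops are censored at withdrawal, with a sensitivity analysis that counts them as not achieved. Counting every withdrawal after application as a failure would overwrite valid times.
5. Compare subgroups by log-rank or worst-rank Wilcoxon in place of the t-test.
6. Report the dressing-failure proportion with an exact 95% confidence interval beside the primary result. This is informative even with no failures: for 0 of 75 the two-sided upper limit is 1 − 0.025^(1/75) = 4.8%.

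The cost is a few sentences in the plan and minor programming. The headline time may become less favourable.

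### The time to haemostasis has no defined start, pressure status, confirmation period, second-dressing clock or failure value, so it may be confounded with compression and is plausibly, but not certainly, biased short

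*Combined protocol and SAP*

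**What the plan says.** The endpoint is defined twice, in the same terms. Primary Outcome has "Time to achieve hemostasis by observing the time at which blood oozing through or from periphery of the dressing stops", and the end of Application of Axiostat has "Time, at which blood oozing through or from periphery of the dressing stops, will be considered as achieving haemostasis".

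The steps around it, all in Application of Axiostat, are:

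- Start: "Remove the sheath and apply Axiostat along with the cotton gauze". This step is not named as time zero.
- Compression: "Apply pressure with fingers for about 5 minutes until dressing adheres to blood on puncture site and stays in position".
- A secondary bandage goes on, with the instruction to "keep Axiostat in position for at least 30 minutes".
- Second dressing: "If bleeding is persistent, then remove the first Axiostat and apply another Axiostat, on puncture bleeding site", and then "Repeat the same procedure of treatment application".
- No haemostasis after two applications is recorded as dressing failure.

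Secondary Outcomes lists rebleeding as a separate item: "Number of patients with rebleeding will be counted". The Statistical Analysis Plan section compares mean haemostasis time between categories by t-test. It does not mention second dressings, failures, censoring or rebleeding. Type of Study gives a single arm. The Training paragraph provides for four catheterization laboratory operators.

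**The concern.** The event is the disappearance of visible oozing, and each dressing is under finger pressure for about the first 5 minutes. Absence of oozing while the site is pressed does not show that it would stay dry on release, yet the definition does not exclude such an observation. The recorded time may then reflect pressure and dressing together.

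The other gaps compound this. Without a time zero, a stated pressure status or a dry confirmation period, trained operators could all comply and still record different times for the same patient. Without a clock rule, a patient who needed two dressings could contribute only the second interval. Without a value for failures, the patients in whom the dressing did not work may simply be absent from the mean. This is the only primary endpoint, and clock times that were not written down cannot be recovered later.

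**Working it through.** **1. The plan's own figures.** Sample Size gives a minimum of 15 patients for a 30% decrease, alpha 0.05, power 0.8. It cannot be reproduced, because no reference mean, SD or sidedness is given. Inverting a one-sample, two-sided normal approximation, CV = 0.30 × √15 / (1.96 + 0.84) = 0.41, which nothing in the documents can confirm. The recruitment figures agree: 75 × 0.9 = 67.5, against about 67. Neither figure says how the time is to be recorded.

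**2. What the definition needs, against what is there.**

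- Time zero: not named. Sheath removal with dressing placement is a candidate only.
- Pressure status when oozing is judged: not stated. The pressure step is tied to adherence of the dressing, not to the endpoint.
- Sustained absence of oozing: not required. A dwell of at least 30 minutes exists but is not linked to the endpoint.
- Second dressing: the treatment step is present, the clock rule absent.
- Two-application failure: the label is present, the value for analysis absent.

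**3. Spread from start point and pressure status.** Take a patient who is dry when pressure is released at about 5 minutes.

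- Clock from placement, judged at release: about 5 minutes.
- Clock from placement, judged during pressure: anything up to about 5 minutes.
- Clock from the end of pressure: 5 − 5 = about 0 minutes.

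All three fit the wording. Judging under pressure, or starting late, shortens the time. Judging only at release makes times heap near 5 minutes, which is too long for anyone whose bleeding stopped earlier. The direction is therefore not fixed by the text.

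**4. Second-dressing clock.** Assumptions that are not in the documents: a share p of patients needs a second dressing; the successful application contributes 5 minutes; the first attempt lasts F = 5 minutes (replaced after the pressure step) or F = 30 minutes (replaced after the dwell).

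Clock continues: mean = (1 − p) × 5 + p × (F + 5) = 5 + pF. Clock restarts: mean = 5.0. Shortfall = pF.

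| p | Patients of 67 | Continuing mean, F = 5 | Shortfall | Continuing mean, F = 30 | Shortfall |
|---|---|---|---|---|---|
| 2% | 1.3 | 5.1 | 0.1 | 5.6 | 0.6 |
| 5% | 3.4 | 5.25 | 0.25 | 6.5 | 1.5 |
| 10% | 6.7 | 5.5 | 0.5 | 8.0 | 3.0 |
| 20% | 13.4 | 6.0 | 1.0 | 11.0 | 6.0 |

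For F = 5 the relative shortfall is 0.5/5.5 = 9% at p = 10% and 1.0/6.0 = 17% at p = 20%. If the clock continues it is zero for every p and F.

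**5. Failures.** A mean taken only over patients with a recorded time leaves out the failures and is shortened. The amount depends on a failure rate that the documents do not give.

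**The case against.** There are several fair points on the plan's side.

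- Finger pressure is one of the listed application steps, so it is part of the treatment under study. That the dressing cannot be separated from compression comes from the single-arm design, and no endpoint wording cures it. This stands. It does not excuse leaving open whether pressure is on or off when the endpoint is read.
- A reader might infer that the endpoint simply measures compression and is biased short. The documents do not support that as a certainty: they never say that oozing is judged under pressure, and step 3 shows that the error can go either way.
- A reader might infer that the second dressing has no rule at all. It has a replacement rule and a two-application failure rule. Only the timing rule is missing.
- A reader might infer that a patient who oozes again keeps the short time. The protocol is silent. The timing sentence follows the steps for persistent bleeding and failure, so it can also be read as meaning that haemostasis is not yet achieved while oozing persists. Rebleeding and quantity of product used are both reported as secondary outcomes.
- A reader might compute that, if times cluster at 5 minutes, any benchmark above 5/0.70 = 7.1 minutes appears beaten by 30% whatever the dressing does. The arithmetic is right, but no reference time is given and the Statistical Analysis Plan section contains no benchmark test.

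These points limit the claim about bias. They do not supply the missing elements of the definition.

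**Conclusion.** The concern holds as a defect of definition. Five elements are missing from the sole primary endpoint: time zero, pressure status at assessment, a sustained-dry condition, the clock through a second dressing, and the value for a failure. As written, a stop under compression can qualify, so the time may be confounded with compression. Short bias is plausible but not demonstrated.

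The size cannot be fixed from the documents. For the second-dressing clock alone it runs from 0.1 to 6.0 minutes over the assumed ranges (2% to 20% needing a second dressing, first attempt of 5 or 30 minutes), and is zero if the clock continues. The 9% and 17% figures are illustrations, because the documents give no second-dressing rate. The point needs settling before data are collected, since compliant operators could otherwise record times that are not comparable.

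**What to change.** Change recording and analysis only. Pressure and treatment steps stay as they are.

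1. Define the endpoint as minutes from placement of the first dressing to the first observation with finger pressure released and no oozing, with no visible oozing recorded during the 30-minute dwell already in the protocol.
2. Run one continuous clock. It does not reset for a second dressing, and it continues if oozing resumes within the dwell.
3. Keep two-application failures in the analysis as not achieving haemostasis, either censored or ranked worst, and not dropped. A t-test of means cannot use such values directly, so the subgroup comparisons need a rank-based or time-to-event method.
4. Times will have a floor near 5 minutes, because pressure must be off. Record each time as an interval (for example, at or before first release) and report the proportion haemostatic at first release beside the median.
5. Keep rebleeding as a separate secondary outcome, and report any re-oozing within the dwell.

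The cost is a few more clock times on the case report form, observation of the site through the dwell, and times that will look longer. The redefinition does not itself change the sample size. The single-arm design will still not separate the dressing from compression, and the report should say so.

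### The plan neither records nor adjusts for which of four operators applied the dressing, so a significant patient-factor t-test may only mark the operator

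*Combined protocol and SAP*

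**What the plan says.** - **Who applies the dressing.** Under Application of Axiostat, the training paragraph says "Training will be rendered to four catheterization laboratory (cathlab) operators for application and direction of use of Axiostat". That only these four apply it is implied, not stated.
- **How it is applied.** The same section describes a manual step: "Apply pressure with fingers for about 5 minutes until dressing adheres to blood on puncture site and stays in position". The primary outcome is the time at which oozing through or around the dressing stops.
- **How times are compared.** The Statistical Analysis Plan section says "Independent sample t-test will be performed to compare the mean of hemostasis time between independent categorical variables". The grouping variables are not named. The other inferential analysis is a correlation: "Pearson correlation analysis will be performed to check the co-relation between primary efficacy endpoint". The threshold is "A P-value of ≤ 0.05 will be considered to be significant".
- **Design.** Type of Study gives a single-arm, single-centre prospective study. Study Population admits both diagnostic and interventional procedures.
- **What is absent.** Nothing says that the operator is recorded, that results are shown by operator, or that any analysis allows for operator.

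**The concern.** Placement and finger pressure plausibly affect when oozing stops, so patients treated by one operator may share technique and stage of learning. Nothing in the design balances patient characteristics across operators. If one operator is both slower and sees more patients with some characteristic (interventional procedures would be a hypothetical example), that characteristic will be associated with haemostasis time even if it has no effect of its own. The planned t-test cannot separate the two explanations.

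These t-tests are the plan's only named group comparisons of the primary endpoint, so a false lead would appear as a finding about which patients the dressing works faster in. If the operator is not recorded, the alternative explanation may be impossible to check afterwards.

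**Working it through.** **The plan's own figures.** 75 × (1 − 0.10) = 67.5, which agrees with about 67 analysed. The plan also says "minimum number of patients needed for study (with alpha 0.05 and power 0.8) was 15 patients" for a 30% reduction, but gives no mean, SD or test, so that figure can be neither confirmed nor refuted. The check below does not depend on it.

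**Inputs.** From the documents: 67 patients, four operators, threshold 0.05 (taken as two-sided). Assumed: patients shared 17/17/17/16, a normal outcome with total variance 1, no true factor effect, and ICC 0.05, 0.10 or 0.20.

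**Formula.** Let c be the number of an operator's patients with the factor and m that operator's total. Let n1 and n0 be the group sizes, and let d = c/n1 − (m − c)/n0 for each operator.
- True variance of the difference in means: ICC × Σd² + (1 − ICC) × (1/n1 + 1/n0).
- The t-test works with approximately 1/n1 + 1/n0.
- With r the ratio of the two, the actual error is about 2[1 − Φ(1.96/√r)].

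**Shares of 20/40/60/80%.** Rounded counts are 3, 7, 10 and 13, so n1 = 33, n0 = 34 and 1/33 + 1/34 = 0.0597. The values of d are −0.321, −0.082, 0.097 and 0.306, so Σd² = 0.213.

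| ICC | True variance | r | Error, formula | Error, simulated (20,000 trials) |
|---|---|---|---|---|
| 0.05 | 0.0674 | 1.13 | 6.5% | 6.6% |
| 0.10 | 0.0750 | 1.26 | 8.0% | 8.2% |
| 0.20 | 0.0903 | 1.51 | 11.1% | 11.3% |

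Drawing each patient's factor status at random with these probabilities, instead of fixing the counts, gives slightly higher values: about 6.5, 9 and 12.5%.

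**Other splits.** Simulated t-test error with fixed counts, at ICC 0.05 / 0.10 / 0.20:
- balanced within operators: 4.7 / 4.1 / 3.7%
- 40/40/60/60%: 4.9 / 5.0 / 4.8% (a little higher if the shares are drawn at random)
- 10/10/90/90%: 10.4 / 15.7 / 25.2%
- two operators against two: 14.3 / 23.3 / 35.6%

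**With operator as a fixed effect.** The error is 4.7 to 5.3% for every split except two against two. There the factor and operator effects cannot be separated.

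**Cost in power when operators do not differ (ICC 0).** Adjustment multiplies the standard error by √[(n1·n0/67) / Σ c(m − c)/m]. Start from 80% power, so the effect is 1.96 + 0.84 = 2.80 standard errors.
- Balanced: the multiplier is 1.00. The only loss is 3 degrees of freedom (65 to 62), at most about 2 points.
- 20/40/60/80%: √(16.75/13.14) = 1.13. Then 2.80/1.13 = 2.48, and Φ(2.48 − 1.96) = 70%. Simulations gave 68 to 70%, a loss of 10 to 12 points.
- 10/10/90/90%: √(16.75/7.04) = 1.54. Then 2.80/1.54 = 1.82, and Φ(1.82 − 1.96) = 44%.

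**The case against.** The strongest reply is that the size of the problem is wholly assumed. The documents give no ICC, no number of patients per operator, no link between operator and case mix, and no named factor. Common training and a scripted application procedure should reduce differences between operators. Operator could itself be one of the unnamed categorical variables. Every such subgroup test is also unadjusted for every other confounder.

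Most of this stands as a limit on magnitude. It does not remove the point. Training reduces variation but does not show that it is absent, and a two-sample t-test neither compares four operators at once nor adjusts another factor for operator. Operator is also the one potential source of confounding that the protocol itself builds in.

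Three stronger readings are tempting, and the documents do not support them:
- **That p-values are generally too small because patients are clustered.** For a factor balanced within operators, the t-test is slightly conservative. The largest errors, 14 to 36%, need a factor that coincides with a two-against-two split of operators, and nothing in the documents suggests one.
- **That an interval for the overall mean would be too narrow.** The plan specifies no such interval. For the mean under these four operators, the ordinary 95% interval covers 95.5, 95.9 and 96.6% in simulation at the three ICCs. Undercoverage arises only when generalising to other operators.
- **That the adjusted model should simply replace the t-test.** When factor and operator are associated but operators do not differ, adjustment loses a material amount of power, so reporting both is easier to defend.

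**Conclusion.** The point holds in a conditional form. The plan has four trained operators apply the dressing by hand, compares non-randomised groups without adjustment, and does not say that the operator is recorded. A false lead needs two things together: operators who differ in haemostasis time, and a factor clearly unevenly spread across them. With 67 patients shared about equally, an assumed ICC of 0.05 to 0.20 and shares of 20/40/60/80%, the nominal 5% error is about 7 to 12%. Without clear imbalance it is near nominal.

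This affects the interpretation of subgroup p-values. It does not bear on a randomised treatment comparison, because there is none, and it does not invalidate the overall haemostasis time observed under these operators. The case for acting rests on the low cost of recording the operator and the difficulty of recovering that information later.

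**What to change.** 1. Add a CRF field for the operator who applied the dressing, with that operator's case number, for every patient.
2. Report haemostasis time by operator.
3. Beside each t-test, report a linear model of haemostasis time on the factor plus operator as a fixed effect. Four operators are too few for reliable random-effect or cluster-robust standard errors; a fixed term needs no variance component.
4. State in the SAP that a factor will not be called significant on the t-test alone if the association disappears after adjustment, and that factors differing only between operators will not be interpreted.

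The cost is one CRF field, a few SAP sentences and 3 degrees of freedom. The power costs worked out above apply to the adjusted estimate. Where factor and operator are closely linked, the adjusted result will be imprecise, so the two estimates and their standard errors should be read together. Loss of significance after adjustment is then not evidence that the factor has no effect.

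### The sample-size statement (15 patients, 30% decrease, 80% power) describes a comparison this single-arm radial trial does not make, so the power attaches to no planned analysis

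*Combined protocol and SAP*

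**What the plan says.** The Type of Study section describes the trial as "Single Arm, Single Centre, Prospective". The Study Population section enrols "Patients who undergo trans radial diagnostic or interventional cardiac procedures". The primary outcome is time to haemostasis.

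The Sample Size section works from reference 1, "with the assumption that Axiostat® will decrease time to haemostasis by 30" per cent, and concludes that the "minimum number of patients needed for study (with alpha 0.05 and power 0.8) was 15 patients". It then says: "A total of 75 patients will recruited, with drop-out rate of 10%, ~ 67 patients will be included in the study". Reference 1 is titled "Usage of chitosan for femoral (USF) hemostasis after percutaneous procedures: a comparative open-label study".

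The Statistical Analysis Plan section lists three things: a Pearson correlation involving the primary endpoint, with no second variable named; independent-sample t-tests of mean haemostasis time between categorical variables that are not named; and descriptive statistics for secondary endpoints. It sets significance at P ≤ 0.05.

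**The concern.** A decrease of 30% needs something to decrease from. With one arm, that has to be a fixed reference time, and the plan states none. The single cited source concerns a different access site and, by its title, a comparative design. The plan does not explain how either carries over.

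The Statistical Analysis Plan section does not supply the missing comparison. Its t-tests compare subgroups of patients who all receive the dressing, and its correlation relates haemostasis time to something unnamed. Neither addresses whether the dressing shortens the time.

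This paragraph is the only justification of the trial's size. A reader could take the final mean haemostasis time as the result of a powered test of a 30% reduction, which the design as written does not contain.

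**Working it through.** **Inputs from the plan.** Effect: 30% relative decrease. Alpha 0.05, sidedness not stated. Power 0.8. Minimum n 15. Recruited 75, drop-out 10%, included about 67. Not given: reference mean, SD, one- or two-sample form.

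**1. Can the 15 be reproduced?** Not directly, because the SD and reference mean are missing. It can only be solved backwards. Let CV be the SD divided by the reference mean, so that the standardised effect is d = 0.30/CV. The normal formula for one sample is n = (CV × (z₀.₉₇₅ + z₀.₈₀)/0.30)², with z₀.₉₇₅ + z₀.₈₀ = 2.80, so n = 15 gives CV = 0.30 × √15/2.80 = 0.41. The noncentral t gives slightly smaller ratios:

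| Reading of 15 | d (two-sided) | CV, two-sided | CV, one-sided |
|---|---|---|---|
| One sample against a fixed value | 0.78 | 0.39 | 0.44 |
| Two groups, 15 per group | 1.06 | 0.28 | 0.32 |
| Two groups, 15 in total (8/7) | 1.57 | 0.19 | 0.22 |

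Six set-ups all return 15, with ratios from 0.19 to 0.44. The plan gives no basis for choosing among them, so the 15 can be neither confirmed nor refuted.

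**2. Does 75 follow from 15?** Drop-out: 75 × 0.9 = 67.5, and 67/0.9 = 74.4, rounded up to 75. That step is right. But 15/0.9 = 16.7, so 15 inflated for drop-out is 17. The move to 75 is unexplained.

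**3. What do 67 patients deliver for estimating the mean?** Half-width of the 95% confidence interval = t₀.₉₇₅,₆₆ × SD/√67 = 1.997/8.185 × SD = 0.244 SD. As a share of the mean, for assumed values of SD/mean:

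| Assumed SD/mean | Half-width, % of mean |
|---|---|
| 0.19 | 5% |
| 0.50 | 12% |
| 1.0 | 24% |

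These ratios are assumptions; the documents give no SD.

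**4. What do 67 patients deliver for the planned tests?** At two-sided alpha 0.05 and 80% power, from the noncentral t with 65 degrees of freedom and noncentrality d/√(1/n₁ + 1/n₂):

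| Subgroup split (assumed) | Detectable difference |
|---|---|
| 34/33 | 0.69 SD |
| 50/17 | 0.80 SD |
| 57/10 | 0.97 SD |

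For the Pearson correlation, by Fisher's z: |r| = tanh(2.80/√(67 − 3)) = tanh(0.350) = 0.34.

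**5. Does the stated 80% carry over to the planned t-tests?** Take d = 0.78, the effect at which a one-sample n of 15 has 80% power. With 67 patients, the subgroup t-test then has power 0.88 (34/33), 0.78 (50/17) or 0.61 (57/10). The power depends on a split the plan does not state.

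**The case against.** The best defence is that 15 is called a minimum, the trial recruits five times as many (75/15 = 5), and a larger sample only raises power for the same test. The plan nowhere says that 67 patients give 80% power. All of this stands, and it rules out two readings a reader might be tempted by.

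- *That the trial is underpowered.* The documents do not show it. A one-sample t-test of a 30% reduction with 67 patients would have power above 0.999 at a CV of 0.4, 0.998 at 0.5, 0.86 at 0.8 and 0.68 at 1.0. No document supports a CV as high as 1.0, and the plan includes no such test.
- *That the drop-out arithmetic is wrong.* It is not. The text applies 10% to 75 and never claims to derive 75 from 15.

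Two further inferences also go beyond the text.

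- *That 15 came from a two-group formula, or that the SD came from the femoral study.* The plan states neither. A one-sample formula against a historical value would suit a single arm, and the 30% is labelled an assumption. Only the title of reference 1 is available here.
- *That a femoral benchmark biases the result.* A comparison of radial times with femoral ones would mix the effect of access site with that of the dressing, but no planned analysis makes that comparison.

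What the defence does not answer is that extra patients raise power only for a test that exists. No reference value and no test of the 30% decrease are specified.

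**Conclusion.** The point holds as an inapplicable power statement. The 15 cannot be reproduced, because implied CVs from 0.19 to 0.44 fit it under different unstated set-ups. The 80% power attaches to no analysis in the plan. The 75 and 67 are consistent with each other but have no stated link to 15.

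This conclusion rests on the plan's own text: a single radial arm, a cited title that is femoral and comparative, and an analysis section with no reference value and no test of a decrease. It does not depend on any assumed SD. The precision and detectable-effect figures rest on about 67 evaluable patients (the plan says included), two-sided 5% testing and roughly normal means; the subgroup splits are illustrative.

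**What to change.** Keep 75 recruited and about 67 included. Remove the 15-patient, 80% power sentence as the justification, and state instead what 67 patients provide:

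- a 95% confidence interval half-width of 0.244 SD for mean time to haemostasis, shown over an assumed range of SD/mean (for example 5% to 24% of the mean for ratios of 0.19 to 1.0);
- for the planned t-tests, at 80% power two-sided, detectable differences of about 0.69, 0.80 and 0.97 SD for splits of 34/33, 50/17 and 57/10;
- for the planned correlation, a detectable |r| of about 0.34.

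Add a sentence saying that no claim of a 30% reduction will be made against the femoral study. Quote one-sample power only if a radial reference value and its test are prespecified in the Statistical Analysis Plan section; without them, it would again be power for an analysis nobody plans to do.

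The cost is one rewritten paragraph and the loss of the 80% power claim. No extra patients are needed and no study procedure changes. Adding a radial benchmark would be a larger change, because both the value and the test would have to be justified.
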